## Study Schedule & Assessments

Study Day	Activity
-7 to -1	Screening, informed consent, baseline questionnaires, recording perception threshold.
0	Randomization; begin first 24 h wash-out (device OFF).
1-5	Period 1 treatment (Active or Sham) + twice-daily electronic diary.
5	24 h wash-out (device OFF).
6-10	Period 2 treatment + diaries.
10	End-of-study visit, adverse event review, exit interview

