## Purpose and Aims

DRG stimulation is today considered a standard therapy for several neuropathic pain conditions. Despite its widespread clinical use, a critical knowledge gap remains: the efficacy of DRG stimulation has never been validated against sham in a controlled trial. The only randomized controlled study conducted to date is an industry-sponsored comparison between DRG stimulation and spinal cord stimulation (SCS) (9), but no trial has directly tested DRG against placebo.

Umeå University Hospital is internationally recognized as a leading center for DRG stimulation. Patients from across Sweden are referred to our department, making our clinic the de facto national referral center for this therapy. In practice, DRG therapy is centralized to our unit. The resulting high patient volumes, together with our long-standing expertise and comprehensive quality database, provide unique opportunities to fill this knowledge gap—opportunities that no other center is currently positioned to offer.

The purpose of this study is therefore to rigorously evaluate whether ongoing sub-threshold DRG stimulation provides genuine analgesic benefit beyond contextual or placebo effects. Sub-threshold programming is already the accepted standard within DRG stimulation, but the specific contribution of this approach remains to be clarified in a placebo-controlled setting. Addressing this knowledge gap will provide robust scientific evidence to support or refute the physiological efficacy of sub-threshold DRG stimulation.

Our primary aim is to determine the impact of sub-threshold DRG stimulation on pain intensity in established responders, using a double-blind, crossover design. Secondary aims include assessing effects on sleep, mood, and activity, as well as evaluating the feasibility of maintaining blinding and capturing safety and tolerability data.

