## Objectives & Hypotheses

- Primary Objective – To compare mean daily pain intensity during five days of sub-threshold DRG stimulation versus sham.
- Secondary Objectives – To compare sleep quality, mood, and daily activity between conditions; to assess safety and tolerability; to explore within-subject carry-over effects.
- Primary Hypothesis – Sub-threshold DRG stimulation will reduce mean Numeric Rating Scale (NRS, 0–10) pain scores compared with sham.

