## Study Design

- Randomized, double-blind, two-period crossover.
- Two treatment arms of 5 days each, separated by a 24 h wash-out.
- Order of conditions (Active → Sham or Sham → Active) allocated 1:1 using computer-generated random blocks.
- Participant, treating clinician, and outcome assessors blinded.

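### Day 5 is scheduled both as Period 1 treatment and as the device-OFF wash-out, and Days 1–10 are 24 h too short for two 5-day arms plus that wash-out

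*Combined protocol and SAP*

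**What the plan says.** In the combined protocol and SAP, Study Design specifies "Two treatment arms of 5 days each, separated by a 24 h wash-out". The primary objective (Objectives & Hypotheses) compares "mean daily pain intensity during five days of sub-threshold DRG stimulation versus sham".

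The table in Study Schedule & Assessments has these rows:
- Day 0: randomisation, and "begin first 24 h wash-out (device OFF").
- Days 1–5: "Period 1 treatment (Active or Sham) + twice-daily electronic diary".
- Day 5: "24 h wash-out (device OFF").
- Days 6–10: "Period 2 treatment + diaries".
- Day 10: "End-of-study visit, adverse event review, exit interview".

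Other sections that bear on the point:
- Data Collection & Management sets the diaries at 09:00 and 20:00.
- Outcome Measures defines the primary outcome over five treatment days, while the Statistical Analysis Plan tests the mean over days 3–5.
- Interventions defines sham as the stimulator being off.
- Randomisation & Blinding Procedures has the programming nurse make every parameter change, and has the analysis scripts run automatically once the last participant finishes Day 10.
- The stopping rule in Safety Monitoring treats the wash-out as a distinct interval before crossover, and measures the pain increase from Day 0.

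**The concern.** Day 5 carries two incompatible labels, and it lies inside the window of the primary analysis. Sham and wash-out are the same physical state. A wash-out entry therefore does harm mainly when it is averaged into an active period, because it pulls that period's mean toward sham. If relief stops as soon as the device is off, only participants in the Active→Sham sequence are affected.

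The trial is intended "to support or refute the physiological efficacy of sub-threshold DRG stimulation", so an avoidable dilution matters most if the result is null. The scripts are predefined and run without intervention, so which entries belong to which period has to be settled before they are fixed. Settling it later would be a post hoc choice.

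**Working it through.** **1. Hours.** Needed: 5 × 24 + 24 + 5 × 24 = 264 h. Available on Days 1–10: 10 × 24 = 240 h. The shortfall is 24 h. The first wash-out starts on Day 0 and frees none of this time. If the day labels are read as elapsed time points with a fixed switching hour, the sequence from Day 0 is 24 + 96 + 24 + 96 = 240 h. It then fits, but each arm is 4 × 24 = 96 h rather than five days.

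**2. Diaries.** Two a day over Days 1–10 gives 20. A 24 h wash-out starting at any quarter-hour on Day 5 contains exactly two of them. The table in step 4 shows which two.

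**3. The plan's own sample size.** Inputs (Statistical Analysis Plan): SD 1.5, difference 1, two-sided α 0.05, power 0.90. The normal approximation is (1.5 × (1.960 + 1.282) / 1)² = 23.6, which rounds up to the stated 24. This reproduces with 1.5 taken as the SD of the paired differences, so that reading is used below. At n = 24 the power is 0.904 by the normal approximation and 0.878 by the exact noncentral t (df 23). The exact figure is the reference here.

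**4. Effect on days 3–5.** Assumptions: true effect 1 point, immediate offset, each diary a point-in-time score, Period 2 treatment lasting through the Day 10 diaries, and equal sequences. With k of six Period 1 entries OFF:
- Active→Sham expected difference = 1 − k/6; Sham→Active = 1.
- Mean difference = 1 − k/12.
- SD = √(1.5² + (half the gap between sequences)²).
- Noncentrality = mean × √24 / SD.

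| Switch-off on Day 5 | Diaries inside the wash-out | k | Active→Sham | Mean | SD | Power |
|---|---|---|---|---|---|---|
| After 20:00 | Day 6, 09:00 and 20:00 | 0 | 1.000 | 1.000 | 1.500 | 0.878 |
| Between the diaries | Day 5 20:00, Day 6 09:00 | 1 | 0.833 | 0.917 | 1.502 | 0.817 |
| Before 09:00 | Day 5, 09:00 and 20:00 | 2 | 0.667 | 0.833 | 1.509 | 0.736 |

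**5. Sensitivity.** The documents give neither an offset time nor a diary recall window. If entries summarise the interval since the previous diary, a midday switch leaves about half of the Day 5 evening interval on treatment. The mean is then 1 − 0.5/12 = 0.96 (power about 85%). Slower offset reduces the loss in the same way.

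**6. Entries outside the window.** The Day 0 wash-out may reach into Day 1, since its hour is not given. The Day 5 wash-out may reach into Day 6. Neither day falls in the SAP's days 3–5 window (Study Days 3–5 and 8–10).

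**The case against.** The best defence is that the Day 0 row lists a wash-out on the day it begins, so the Day 5 row can be read the same way. Day 5 is then a transition day, the overlap disappears, and each arm touches five calendar days. This stands as a possible reading, but it leaves 96 h of treatment per arm against the five days in the objective, the design and the outcome definition. It also still depends on an hour that is not stated.

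A second defence is that the outcome is limited to treatment days and the analysis compares treatment periods, so wash-out entries are excluded by implication. A reader might infer that the plan intends to count OFF entries as active treatment. The documents do not say that. They also do not say how an automated script should treat entries on a day that carries both labels. The only data-handling rules, carry-forward after an aborted period and multiple imputation, do not remove an observed entry.

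Third, switch-off after the 20:00 diary is the reading closest to the table and costs the primary analysis nothing. That is correct. It would need a nurse session after 20:00, however, and no session hour is given; a daytime session would fall between the diaries.

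A reader might also infer a much larger power loss by combining switch-off before 09:00 with Day 10 diaries that are counted after Period 2 has ended. The documents do not support that combination. An early switch leaves no on-treatment diary on Day 5, which makes it the least plausible hour, and the table assigns Days 6–10 to treatment.

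**Conclusion.** The inconsistency is real and should be corrected before enrolment. The schedule is 24 h short of the stated design, two of the 20 diaries always fall in the Day 5 wash-out, and no switching hour or explicit exclusion rule is given.

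The effect on the primary analysis is conditional. Under the assumptions in the working it is nil for a switch after 20:00, 0.08 point for a switch between the diaries, and 0.17 point for a switch before 09:00. Slower offset or interval recall makes it smaller. A reader might infer that the error could produce a spurious benefit. It could not, because the bias runs only toward no difference. The sample size of 24 is not in question on this point.

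**What to change.** Make Objectives & Hypotheses, Study Design, Randomisation & Blinding Procedures, Study Schedule & Assessments, Outcome Measures, the Statistical Analysis Plan and Safety Monitoring agree. The choice between two options is for the investigators.

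- **Option A: a separate wash-out day.** Period 1 on Days 1–5, wash-out on Day 6, Period 2 on Days 7–11, final visit and data lock moved to Day 11. Both periods start and end at the same clock hours, so they are equal in length. For example, starting before 09:00 on the first day and ending after 20:00 on the fifth gives about 4 × 24 + 12 = 108 h and ten on-treatment diaries per period. The gap is then about 36 h, and the text should say so. The SAP window becomes Study Days 3–5 and 9–11. The Day 0 baseline for the stopping rule must be recorded before the first switch-off; otherwise it may fall inside the wash-out.
- **Option B: keep Day 10.** State periods of 4 × 24 h and a switching hour that leaves the SAP window fully on treatment. Switching after the 20:00 diary on Days 0, 1, 5, 6 and 10 does this. The wash-outs then cover the Day 1 and Day 6 diaries, and each period has eight on-treatment diaries (Days 2–5 and 7–10). Reword the five-day objective and outcome to match.

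Under either option, before the scripts are fixed, define each period's analysis window from the time-stamped session that starts it to the one that ends it. Log a session in sham periods too. Exclude entries made during a wash-out or after Period 2 ends.

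The cost is wording, a logged session in sham periods, and at most one extra study day. Diary entries and parameter changes are already time-stamped. Early or late sessions need staff at those hours; if that is impractical, the time-stamp exclusion also works with daytime sessions, provided the analysis window is redefined to match.

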## Outcome Measures

Category	Measure	Time-Points
Primary	Average NRS pain (0–10) across 5 treatment days	Daily AM & PM
Secondary	Sleep quality (5-point PGIC)*	Daily AM
	Mood (5-point PGIC)*	Daily PM
	Daily activity (5-point PGIC)*	Daily PM
	Adverse events	Continuous
Exploratory	Device usage logs, rescue medication use	Daily

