## Statistical Analysis Plan

- Sample Size – Assuming within-subject SD = 1.5 NRS points, minimally important difference = 1 point,  $\alpha = 0.05$ , power = 0.90, two-sided paired test → 24 completers needed (calculated with G\*Power). To accommodate 15 % attrition, target enrolment = 28.
- Primary Analysis – Paired t-test (or Wilcoxon signed-rank if non-normal) comparing mean NRS pain across days 3–5 between Active and Sham periods. If a period is aborted due to high pain, the last recorded score will be carried forward for the remaining days. Treatment order and carry-over tested via mixed-effects model with fixed effects for treatment, period, and sequence.
- Secondary Outcomes – Similar within-subject comparisons; Bonferroni correction applied.
- Missing Data – Multiple imputation if > 5 % diary fields missing.

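### Sleep, mood and activity are rated daily on a change scale with no visible comparison point, so a real effect could be diluted or made to depend on sequence

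*Combined protocol and SAP*

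**What the plan says.** The secondary objective (Objectives & Hypotheses) is "To compare sleep quality, mood, and daily activity between conditions". The Outcome Measures table measures the three domains with "Sleep quality (5-point PGIC" each morning, and "Mood (5-point PGIC" and "Daily activity (5-point PGIC" each evening. All three rows carry an asterisk, but no footnote appears in the available text. Pain, in the same table, is a 0–10 numeric rating.

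The Statistical Analysis Plan covers the secondary outcomes in one line: "Similar within-subject comparisons; Bonferroni correction applied". It gives them no summary measure or day window. For the primary outcome it specifies "comparing mean NRS pain across days 3–5 between Active and Sham periods", whereas the Outcome Measures table averages pain over all 5 treatment days.

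Data Collection & Management gives the diary times (09:00 and 20:00) but not the item wording. The schedule contains "Screening, informed consent, baseline questionnaires, recording perception threshold" on days -7 to -1, then on day 0 "Randomization; begin first 24 h wash-out (device OFF", and a second 24 h OFF interval between the periods. None of these is named as the reference for the PGIC.

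**The concern.** The plan does not spell out PGIC. In its standard meaning it is the patient's global impression of change, and a change rating has meaning only relative to a reference. This design offers at least four natural ones: the previous day, the OFF wash-out just before the period, the pre-study state on usual therapy, and the previous treatment period. What precedes the two periods also differs. Period 1 follows usual therapy plus 24 h OFF; Period 2 follows the other condition plus 24 h OFF. Without an instruction, patients may choose differently, and one patient may change reference from day to day.

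All three secondary efficacy outcomes use this scale. If patients compare with yesterday, a stable worsening under sham soon reads as no change, and a real difference is lost. If they compare with the previous period, the size of the effect depends on sequence. The reference exists only in the patient's mind when the item is answered, so it cannot be reconstructed once the dataset is locked.

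**Working it through.** **The plan's own figure.** No sample size or effect size is stated for the PGIC outcomes. The 24 completers concern NRS pain only: ((1.960 + 1.282) × 1.5 / 1)² = 23.64, rounded up to 24 by the normal approximation. (The exact two-sided paired t calculation gives 26, a separate matter.) Nothing below changes that number.

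**Inputs from the plan.** Two 5-day periods, 24 h OFF before each, 1:1 sequences, daily ratings. Both windows are shown, days 3–5 and days 1–5, because the window for the secondary outcomes is not stated.

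**Assumptions, not from the plan.** The state is constant within each period. On a category scale, usual therapy = 0, Active = 0 and Sham = OFF = -1, so the true Active-minus-Sham difference is 0 - (-1) = 1. There is no floor or ceiling.

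**Formula.** Rating = current state minus reference state. Effect = mean rating in Active minus mean rating in Sham.

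- *Yesterday.* Active: first day 0 - (-1) = 1, then 0. The mean is 1/5 = 0.2 over days 1–5 and 0 over days 3–5. Sham: -1 - (-1) = 0 on every day. Effect: 0.2 or 0.
- *Pre-study state.* Active 0 - 0 = 0; Sham -1 - 0 = -1. Effect: 1.
- *Preceding wash-out.* Active 0 - (-1) = 1; Sham -1 - (-1) = 0. Effect: 1.
- *Previous period (Period 1 against usual therapy).* Active→Sham: Active 0 - 0 = 0, Sham -1 - 0 = -1, effect 1. Sham→Active: Sham -1 - 0 = -1, Active 0 - (-1) = 1, effect 2.

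| Reference | Active→Sham | Sham→Active | Average at 1:1 |
|---|---|---|---|
| Yesterday, days 3–5 | 0 | 0 | 0 |
| Yesterday, days 1–5 | 0.2 | 0.2 | 0.2 |
| Pre-study state | 1 | 1 | 1 |
| Preceding wash-out | 1 | 1 | 1 |
| Previous period | 1 | 2 | (1 + 2)/2 = 1.5 |

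If the pre-study state is instead set equal to OFF, the two sequences swap values in the last row and the average stays 1.5.

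**Sequence effect.** With the previous-period reference, the mean rating over both periods is (0 - 1)/2 = -0.5 for Active→Sham and (-1 + 1)/2 = 0 for Sham→Active. If the plan's mixed model were applied to these outcomes, this 0.5 difference would appear as a sequence effect although the model contains no carry-over. Exploring carry-over is itself a stated secondary objective.

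**Check under no effect.** Set Active = Sham = OFF = -1 and usual = 0. Yesterday, pre-study and wash-out references each give an effect of 0. The previous-period reference gives -1 - 0 = -1 in Active→Sham and 0 - (-1) = 1 in Sham→Active, which average to 0 when sequences are balanced.

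**The case against.** The strongest reply is that the anchor may already be in the plan. A footnote attached to exactly these three rows is the natural place for it, and its absence from machine-read text is not evidence of an omission. The baseline questionnaires also offer a plausible common anchor. This stands: the point is conditional on the footnote, and the sponsor can settle it by producing the footnote and the item wording.

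Three stronger readings might be inferred, and the documents support none of them.

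- *That a PGIC is unsuitable in itself.* A reference common to both periods cancels in the within-subject difference: the pre-study row returns exactly 1. The line on secondary analyses fits such change scores as well as it fits levels.
- *That the trial estimate could run from zero to double.* The value 2 arises in one sequence only. With 1:1 allocation the average cannot exceed 1.5 in this illustration. Exact zero needs the days 3–5 window, which the plan states only for the primary outcome. Two of the four references give the right answer.
- *That a positive result could not be interpreted.* Under no effect every reference gives a mean difference of 0 with balanced sequences. In this model, an unclear reference distorts size and can hide an effect, but does not create one on average.

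What remains is that no reference is visible, that this design makes the choice matter, and that the same diary already uses a state rating for pain.

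**Conclusion.** The point holds as a cheap improvement to three secondary outcomes. Unless the missing footnote fixes one reference for both periods, a true difference of 1 category could appear as anything from 0 to 1.5 on trial average, and could differ between sequences. These figures illustrate the mechanism under the assumed states; they do not predict the trial's result. The conclusion also rests on PGIC having its standard meaning. The finding most at risk is a null one, mainly if patients compare with yesterday. The primary pain outcome and the sample size are untouched.

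**What to change.** First, supply the footnote and the exact wording of the three items. If they do not settle the reference, then before the first participant reword the items as ratings of the current state at the same diary times: last night's sleep in the morning, today's mood and today's activity in the evening, for example on a 0–10 NRS as for pain. State the day window and compare period means.

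If PGIC is kept, put one fixed reference common to both periods into the item, for example the week before the study, and state the summary measure. This recovers the true difference apart from floor or ceiling limits of a 5-point scale.

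The cost is rewording three eDiary items. The number of entries, the form of the analysis and the sample size do not change. With the state ratings, the small downside is less comparability with any clinic data collected as PGIC.

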## Data Collection & Management

All study data *remain entirely* inside Patientkollen®’s two mirrored on-premises physical servers located in secure Swedish data centres—no exports, downloads, or external copies are made during the trial. The analysis workspace is hosted *within* this mirrored infrastructure under read-only permissions.

- Randomization module – generates concealed allocation; visible only to the programming nurse.

- eConsent – digital Participant Information Sheet and Bank-ID e-signature; signed PDFs stored in-platform.
- eDiary – questionnaires (pain, sleep, mood, activity) are scheduled at 09:00 and 20:00 daily; SMS and e-mail prompts are sent, followed by an automated reminder after 1 h if still incomplete.
  - Missing > 2 consecutive diaries triggers an investigator alert.
- Real-time dashboards – colour-coded indicators flag missing entries and SAE alerts for investigators and the DSMB.
- Locked analysis workspace – pre-specified statistical scripts execute within Patientkollen on read-only copies of the dataset; a complete audit trail is archived.
- Comprehensive audit logging – every action by patients and study personnel (e.g., diary entry, parameter change, data review) is time-stamped and written to an immutable audit log within Patientkollen.

All data are encrypted at rest and in transit on the mirrored servers, which operate under ISO 27001-compliant security policies with role-based access control.

## Statistical Analysis Plan

- Sample Size – Assuming within-subject SD = 1.5 NRS points, minimally important difference = 1 point,  $\alpha = 0.05$ , power = 0.90, two-sided paired test → 24 completers needed (calculated with G\*Power). To accommodate 15 % attrition, target enrolment = 28.
- Primary Analysis – Paired t-test (or Wilcoxon signed-rank if non-normal) comparing mean NRS pain across days 3–5 between Active and Sham periods. If a period is aborted due to high pain, the last recorded score will be carried forward for the remaining days. Treatment order and carry-over tested via mixed-effects model with fixed effects for treatment, period, and sequence.
- Secondary Outcomes – Similar within-subject comparisons; Bonferroni correction applied.
- Missing Data – Multiple imputation if > 5 % diary fields missing.

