## Preliminary Results

Umeå University Hospital is internationally recognized as one of the leading centers in the world for DRG stimulation. Over the past decade, our department has established a comprehensive quality database with structured, prospective data collection, including patient-reported outcome measures (PROMs), patient-reported experience measures (PREMs), detailed device and implant information, and systematic adverse event reporting.

This database currently includes more than 100 patients with active DRG therapy, representing what is likely the largest clinical cohort worldwide. The longest follow-ups now exceed five years (Appendix 1: Data report from our quality database). Analyses of these data indicate that DRG stimulation is a safe and effective treatment for a broad spectrum of neuropathic pain conditions, with consistent and long-lasting analgesic effects. Our findings further suggest that treatment durability extends beyond pain reduction, positively influencing function, mood, and quality of life. Importantly, a comprehensive retrospective analysis of these data is being finalized and will be published during the second half of 2025, further underscoring the robustness and maturity of our clinical experience.

This extensive real-world experience and infrastructure provide a unique foundation for the proposed trial, ensuring feasibility, robust recruitment, and reliable follow-up. Moreover, our track record demonstrates both the scientific and clinical capability of our team to conduct a sham-controlled study of this scope with high internal validity.

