## Appendix 1: Data report from our quality database for patients with DRG stimulation therapy

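### The stated 90 % power at 24 completers is slightly high for the planned paired t-test: with 1.5 as the SD of the paired difference it is 87.8 %, and 90 % needs 26 completers or a between-period correlation that the plan does not state

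*Combined protocol and SAP*

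**What the plan says.** The Sample Size item of the Statistical Analysis Plan gives its inputs as "Assuming within-subject SD = 1.5 NRS points, minimally important difference = 1 point", with alpha 0.05 and "power = 0.90, two-sided paired test". Its result is "two-sided paired test → 24 completers needed". It names G*Power as the software and sets enrolment at 28 to allow for 15 % attrition.

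The Primary Analysis item that follows names the test: "Paired t-test (or Wilcoxon signed-rank if non-normal) comparing mean NRS pain across days 3–5".

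The sample-size item gives no between-period correlation, no source for 1.5 and no software settings. The Preliminary Results section points to "Appendix 1: Data report from our quality database", but only the heading of that appendix is in the text available for this review. A source for the SD may be there; that could not be checked.

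**The concern.** A paired t-test estimates the SD of the differences from the data. With about two dozen participants this costs some power compared with a calculation that treats the SD as known. The stated 24 matches the known-SD calculation, which suggests that the 90 % does not belong to the test the plan will use.

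The label on the SD adds a second difficulty. A within-subject SD in a crossover can mean the SD of the paired difference, or the residual SD of one period. Some authors also use the term loosely for the total SD of a single-period score. These readings give different power at the same 24 completers, so a reader cannot confirm the 90 % from what is written. The sentence is likely to be carried into the registration and the publication as 90 % power, and it should be reproducible for the named test.

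**Working it through.** **Inputs, all from the Sample Size item:** difference 1 NRS point, SD 1.5, two-sided alpha 0.05, power 0.90, 24 completers, 15 % attrition, 28 enrolled.

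**Step 1. Reproduce the plan's figure.** Take 1.5 as the SD of the paired difference and use the normal approximation:

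n = ((z₀.₉₇₅ + z₀.₉₀) × SD / difference)² = ((1.960 + 1.282) × 1.5 / 1)² = 23.64, so 24.

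Normal-approximation power at 24 is Φ(√24 / 1.5 − 1.960) = Φ(1.306) = 90.4 %. The stated number is reproduced.

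**Step 2. Repeat for the named test.** For a two-sided paired t-test, power comes from the noncentral t distribution with n − 1 degrees of freedom and noncentrality √n × 1 / 1.5:

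| Completers | Power |
|---|---|
| 23 | 86.3 % |
| 24 | 87.8 % |
| 25 | 89.2 % |
| 26 | 90.4 % |
| 28 | 92.5 % |

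A simulation of 400,000 trials agrees: 87.9 % at 24 and 90.5 % at 26. Using n − 2 degrees of freedom, as in a crossover analysis with a period effect, gives 87.7 % at 24 and still requires 26. The largest SD of the difference that gives 90 % at 24 is 1.447. Equivalently, with SD 1.5 the difference detectable at 90 % power is 1.5 / 1.447 = 1.04 points, against the planned 1.00.

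**Step 3. Try 1.5 as the total SD within a period.** The SD of the difference is then 1.5 × √(2(1 − r)), where r is the between-period correlation. The documents give no r, so it is an assumption and a range is shown:

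| r | SD of difference | Power at 24, paired t |
|---|---|---|
| 0.3 | 1.775 | 75.3 % |
| 0.4 | 1.643 | 81.5 % |
| 0.5 | 1.500 | 87.8 % |
| 0.535 | 1.447 | 90.0 % |
| 0.6 | 1.342 | 93.8 % |

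The exact calculation returns 24 as the required number only for r between 0.535 and 0.556. The lower limit is 1 − 1.447² / (2 × 1.5²) = 0.535. The upper limit comes from the SD of the difference at which 23 completers already suffice, 1.413: 1 − 1.413² / (2 × 1.5²) = 0.556. At r = 0.5 the SD of the difference is 1.5 again and Step 2 applies.

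**Step 4. Sensitivity only.** If 1.5 were the residual SD of one period, the SD of the difference would be 1.5 × √2 = 2.12 and power at 24 would be 60.0 %. The documents do not show that this is what was meant.

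**Step 5. Does enrolment cover the gap?** At the plan's own attrition, 28 × 0.85 = 23.8 completers are expected, which is below 26.

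**The case against.** The strongest reply is that 24 follows from a standard formula with the stated inputs, that 26 is only two participants away, and that a 2-point difference in power is small beside the uncertainty in any assumed SD. On this view the plan has an undefined input, not a wrong figure, since a correlation of 0.535 or more would make 90 % correct. It can also be said that the G*Power settings are unknown, so how 24 arose is unknown.

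Much of this stands. The gap is small, it depends on how the SD is read, and nobody can tell from the document which calculation was run. It also stands that a total SD within a period fits the plan's label poorly, and that the residual reading fits it at least as well.

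These points do not rescue the stated power. The normal approximation is not the test the plan names. The correlation that would support 90 % is an input the plan does not give. The residual reading only lowers the power. No reading gives 90 % at 24 for the paired t-test from the stated inputs alone.

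**Conclusion.** The concern holds and is minor. With 1.5 as the SD of the Active-minus-Sham difference, the planned two-sided paired t-test has 87.8 % power at 24 completers against 90 % stated, and 26 completers are needed for 90.4 %. This assumes approximately normal differences and a true difference of 1 point. With 1.5 as a total SD within a period, 90 % is reached at 24 only with a correlation of about 0.535 or more.

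The arithmetic is certain. The meaning and source of the SD are open, and the unseen content of Appendix 1 may settle them. The consequence for the trial is small: the design remains reasonably powered on the first reading, and the correction is to what is claimed for it.

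**What to change.** First say which SD 1.5 is and where it comes from, citing the Appendix 1 data report if that is the source. Then use one of two sentences.

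- If it is the SD of the paired difference: *24 completers give about 88 % power for a two-sided paired t-test at a 1-point difference, with 1.5 the SD of the Active-minus-Sham difference in the primary-window mean NRS, taken from [source].*
- If it is the total SD within a period: keep 90 %, and state the between-period correlation that supports it (about 0.535 or more) with its source.

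If the sponsor finds that 1.5 is a residual SD for one period, neither sentence applies and the power must be restated from an SD of the difference of 2.12.

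For either of the two sentences, the cost is one sentence of SAP text, with no added enrolment and no change to the analysis. On the first, the quoted power falls from 90 % to about 88 %.
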